## **6.2. Safety**

The safety profile will be evaluated in terms of frequency counts and percentage of patients experiencing specific events falling into one of the following four categories:

- Immediate reactions occurring within 30 minutes after vaccination will be listed at the participant-level and summarized by group.
- Solicited signs and symptoms occurring greater than 30 minutes after receipt of the booster dose through 7 days post vaccination will be listed at the participant-level and summarized by severity for Groups A and B. Exact 95% CI will be provided.
- All other adverse events occurring within 28 days of the booster dose will be listed at the participant-level and summarized by severity and relationship to study vaccines for Groups A and B.
- SAEs occurring within 28 days of the booster dose will be listed at the participant-level and summarized by severity and relationship to study vaccines for Groups A and B.

## **6.3. Analysis sets**

All immunogenicity analyses and summaries will be performed on the intention-to-treat (ITT) basis which will be considered as the primary approach to immunogenicity analyses. Per protocol (PP) analyses will also be conducted on all enrolled participants. Safety analyses will be conducted on the ITT basis. Analyses set definitions are provided below.

### **6.3.1. Intention-to-Treat analysis set**

The ITT analysis will be conducted for analyses of serology using all enrolled participants in this study whether the participant took the booster dose or not. According to this analysis set, long-term assessment of the anti-JE antibody response to CD-JEV is evaluated using all participants enrolled in the study with at least one serology result in Year 3 or Year 4 prior to the booster dose. The ITT analysis set will be used to analyze the primary and secondary serology objectives.

### **6.3.2. Per-Protocol analysis set**

A participant is valid for the PP analysis set if s(he) satisfies the inclusion/exclusion criteria of the study at Visit 01, has a valid serology result at Year 3 (Visit 01) and Year 4 (Visit 02) prior to vaccination, and had no significant deviation in blood collection at the two time points. The PP analysis set will be used to analyze the primary and secondary serology objectives.

### **6.3.3. Safety analysis set**

The safety analysis set will include all enrolled participants who had the booster dose and will be used to analyze all safety measurements including solicited/ unsolicited AEs and SAEs collected in the study.

## **7. DATA SAFETY MONITORING PLAN**

### **7.1. Assessment of safety**

#### **7.1.1. Specification of safety parameters**

Study vaccine safety profiles will be parameterized as the proportion of participants experiencing specific adverse events categorized into one of the following four categories:

- Immediate reactions occurring within 30 minutes of booster dose, as observed by study staff or reported by the participant to study staff.
- Solicited signs and symptoms occurring greater than 30 minutes after the booster dose through 7 days post vaccination, as observed by study staff or reported by the participant to study staff.
- All other adverse events occurring within 28 days of receipt of the booster dose as observed by study staff or reported by the participant's parents to study staff.
- All SAEs occurring within 28 days of receipt of the booster dose.

### **7.2. Methods and timing for assessing, recording, and analyzing safety parameters**

#### **7.2.1. Adverse events**

An adverse event is defined as any untoward medical occurrence in a patient or clinical investigation participant administered a pharmaceutical product which does not necessarily have a causal relationship with this treatment. An AE can therefore be any unfavorable and unintended sign (including an abnormal laboratory finding), symptom, or disease temporally associated with the use of a medicinal product, whether or not considered related to the medicinal product. The occurrence of an AE may come to the attention of study personnel during study visits and interviews of a study participant presenting for medical care.

Information to be collected on adverse events includes event description, time of onset, clinician's assessment of severity, relationship to study product (assessed only by those with the training and authority to make a diagnosis), and time of resolution/stabilization of the event.

Any medical condition that was present at the time that the patient was enrolled should not be reported as an AE. However, if it deteriorates during the study safety recording periods, it should be recorded as an AE.

AEs should be graded for severity and relationship to vaccine.

#### **7.2.1.1. Severity of event**

Any AE which is not a local and systemic sign or symptom occurring within 7 days post booster dose will be assessed by the clinician to quantify intensity using the following guidelines:

Grade	Categorization	Definition
Grade 1	Mild	Symptoms causing no or minimal interference with usual social and functional activities.
Grade 2	Moderate	Symptoms causing greater than minimal interference with usual social and functional activities.
Grade 3	Severe	Symptoms causing inability to perform usual social and functional activities with intervention or hospitalization indicated.
Grade 4	Potentially life-threatening	Symptoms causing inability to perform basic self-care functions OR medical or operative intervention indicated to prevent permanent impairment, persistent disability, or death.

*\*Intervention defined as Medical, surgical, or other procedures recommended or provided by a healthcare professional for the treatment of an adverse event.*

Changes in the severity of an AE should be documented to allow an assessment of the duration of the event at each level of intensity to be performed. Adverse events characterized as intermittent require documentation of onset and duration of each episode.

### 7.2.2. Relationship to study vaccines

The clinician's assessment of an AE's relationship to test vaccine is part of the documentation process, but it is not a factor in determining what is or is not recorded in the study. If there is any doubt as to whether a clinical observation is an AE, the event should be recorded. All AEs must have their relationship to study vaccines assessed using the following guidelines:

Categorization	Definition
Definitely Related	An adverse event or unanticipated problem clearly related to the research procedures.
Possibly Related	There is a reasonable possibility that the adverse event, incident, experience, or outcome may have been caused by the procedures involved in the research.
Not Related	Any adverse event or unanticipated problem clearly not related to study procedures.

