### 3.5. Potential risks and benefits

#### 3.5.1. Potential risks

The child may experience discomfort and pain from venipuncture for collection of 2 ml of blood. Venipuncture is sometimes associated with discomfort during phlebotomy, and rarely, an infection at the site of phlebotomy if improperly conducted. The child may experience discomfort, pain, redness, swelling, and/or local hardness at the injection site.

Like any vaccine, vaccination with CD-JEV may cause side effects in some children. The side effects of JE vaccination may include pain at the injection site for a short while after injection and swelling, redness, and tenderness at the injection site. Fever may occur and in some cases a rash may appear in the initial days following the vaccination. Because the vaccine is a live attenuated vaccine, there is a very small theoretical risk that encephalitis, or infection of the brain, could occur. However this has never been reported to occur with CD-JEV. Allergic reactions and death, while rare, are also possible with any vaccination.

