7.2. Analysis of Safety endpoints

- The number and proportion of participants with at least one occurrence of an immediate reaction (local or systemic reaction, unsolicited AE, and SAE) occurring within 30 minutes of the booster vaccination will be tabulated by study group. The severity, relationship to the booster vaccination, status at 30 minutes (ongoing or not), medication given, and total number of the immediate reactions will be summarized by study group as well. Proportion of participants

will be based on the number of participants who are in safety analysis set. In addition, the immediate reaction will be listed at the participant-level.

- The number and proportion of participants with at least one occurrence of local reactions (ecchymosis, erythema, edema, induration, and pain/tenderness) and with at least one occurrence of systemic reactions (fever, change in eating habits, diarrhea, sleepiness, irritability, unusual crying, and vomiting) occurring greater than 30 minutes after receipt of the booster dose through 7 days post vaccination will be summarized by study group along with 95% CI of the percent. Each specific local or systemic reaction will be summarized by severity for each study group. A listing including the local and systemic reactions at the participant-level will be provided as well.
- The number and proportion of participants with at least one unsolicited AE occurring within 28 days of the booster dose along with 95% CI of the proportion will be presented by study group. The AEs will be summarized by maximum severity and relationship to the booster vaccination for each study group. The total number, maximum severity, relationship to the booster vaccination, onset date, status/outcome, duration for resolved cases (resolution date – onset date + 1), and medication given of AEs will be also summarized by study group. Summaries will be repeated for AEs found to be related the booster vaccination. A listing of AEs at participant-level will be presented.

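### The relatedness scale in Protocol 7.2.2 is worded for study procedures, so blood-draw events can be reported in SAP 7.2 as related to the booster

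*Protocol*

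**What the plan says.** Protocol 7.2.2 is headed as a rating of relationship to study vaccines, and its instruction is explicit: "All AEs must have their relationship to study vaccines assessed using the following guidelines". Section 7.2.1 says the same: "AEs should be graded for severity and relationship to vaccine".

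The three definitions that follow use a different reference:

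- *Definitely Related*: "An adverse event or unanticipated problem clearly related to the research procedures".
- *Possibly Related*: a reasonable possibility that the event "may have been caused by the procedures involved in the research".
- *Not Related*: "Any adverse event or unanticipated problem clearly not related to study procedures".

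There is no category for an event caused by a procedure other than vaccination. Section 7.2.2 also says of the relatedness assessment that "it is not a factor in determining what is or is not recorded in the study", so an event is recorded whatever its cause. Section 7.2.4 sends SAEs to the same scale.

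Venipuncture is a study procedure with acknowledged harms. Section 3.5.1 says "The child may experience discomfort and pain from venipuncture for collection of 2 ml of blood", and adds a rare risk of infection at the site.

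SAP 7.2 reports the rating as relationship to the booster vaccination for immediate reactions, unsolicited AEs and SAEs. It then adds, for AEs, "Summaries will be repeated for AEs found to be related the booster vaccination", with a matching sentence for SAEs. It gives no rule for setting procedure-related events aside.

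**The concern.** The question put to the assessor and the definitions offered as answers do not have the same scope. The question concerns the vaccine. The definitions cover everything done to the child for the study, which includes vaccination and the blood draws. The protocol elsewhere treats these as two sources of harm: section 7.2.3, on free medical care, names the study vaccine and the study procedure as alternatives.

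At stake are the related-event summaries of the booster. The trial is open-label without a placebo arm, so these summaries are read as absolute frequencies, and no control group would show how many of the events came from the blood draws. A second cost is inconsistency: two assessors can both comply with section 7.2.2 and code the same event differently.

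**Working it through.** The documents state no figure on this point, so there is none to reproduce. The check is mainly a comparison of texts, followed by an illustration.

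**1. One event, two readings.** Take an infection at the phlebotomy site after the Day 7 draw, which the clinician is sure has nothing to do with the vaccine.

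| Text followed | Question answered | Code |
|---|---|---|
| Heading and instruction of 7.2.2; 7.2.1; 7.2.4 | Is it related to the vaccine? | *Not Related* |
| Category definitions of 7.2.2 | Is it related to study procedures? | *Definitely Related* |

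The two readings fall at opposite ends of the scale. Under the second, *Not Related* is unavailable because the event is clearly related to a study procedure. SAP 7.2 would then count it as related to the booster.

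**2. Which draws matter.**

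- Visit 02: Protocol 4.4.3 lists the draw before the booster at the same visit. A complaint that appears after vaccination can enter the 30-minute immediate-reaction summary, which SAP 7.2 breaks down by relationship, or the 28-day AE summary.
- Visit 09 (7 to 10 days after the booster): the draw falls well inside the 28-day window.
- Visit 10 (21 to 35 days after the booster): this is the exit visit, and Protocol 4.4.6 lists the AE enquiry before the draw. Little from this draw would be captured.

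**3. Which outputs matter.** Affected: the relationship breakdowns for immediate reactions, AEs and SAEs, and the repeated summaries of related AEs and SAEs. Not affected: the counts of children with any AE or SAE, since recording does not depend on relatedness. Largely unaffected: solicited reactions after 30 minutes. The local ones are confined to the injection site, and SAP 7.2 summarizes each reaction by severity, not relationship.

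**4. Illustration of size.** The documents give no rate of recorded blood-draw events. I assume 0.1%, 0.5% or 2% per draw.

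Children: at most 818 (Protocol 5). SAP 2.3 expects 10% to 40% of these not to be enrolled: 818 × 0.9 = 736 and 818 × 0.6 = 491. These are enrolled children; Visit 02 exclusions and losses would make the number boosted smaller.

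Expected events = children × draws × rate per draw. Each range runs from 491 to 818 children.

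| Assumed rate per draw | Day 7 draw only | Visit 02 and Day 7 draws |
|---|---|---|
| 0.1% | 0.5 to 0.8 | 1.0 to 1.6 |
| 0.5% | 2.5 to 4.1 | 4.9 to 8.2 |
| 2% | 9.8 to 16.4 | 19.6 to 32.7 |

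For example, 491 × 2 × 0.005 = 4.9 and 818 × 2 × 0.005 = 8.2. At 0.5% per draw, the chance of at least one event from the Day 7 draw is 1 − 0.995^491 = 0.92 to 1 − 0.995^818 = 0.98.

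At each assumed rate these are ceilings for the two draws: they suppose that every child is boosted, every event is recorded in the window, and every assessor follows the definitions over the heading.

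**The case against.** The strongest reply is that the intent is plain. The heading, first sentence and instruction of 7.2.2, together with 7.2.1 and 7.2.4, all name the vaccine or product, and 7.2.1 reserves the rating for people trained and authorized to make a diagnosis. Such a clinician is unlikely to blame the booster for a phlebotomy-site infection. This stands, and it limits the point to what can happen. A reader might infer that blood-draw events will be counted as booster-related; the documents do not support that, because the result depends on which text each assessor follows.

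Other stronger inferences also fail:

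- *The definitions leave out the vaccine.* Giving the booster is itself a study procedure. The definitions are too broad, but they do not exclude it.
- *The two kinds of event cannot be separated at analysis.* Section 7.2.1 collects a description and time of onset for each event, and SAP 7.2 plans participant-level listings. Separation is possible, but no rule for it is specified in advance.
- *DSMB oversight is compromised.* Section 7.3.1 sends every SAE to the DSMB regardless of relatedness. Only the real-time review in 7.4.2 depends on suspected relatedness, and its trigger names the product.
- *The secondary safety objective rests on this code.* That objective is the safety profile. None of the endpoints listed in Protocol 2.4 or SAP 7.1 is defined by relatedness, which enters as a further breakdown.

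It is also fair to say that the error would overstate vaccine-related events, which is the cautious direction, and that both groups have the same draws, so no bias between A and B is shown. What remains is that the definitions do not match the question they serve, and the tables depend on those definitions.

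**Conclusion.** The point holds as a wording defect with modest consequences. Section 7.2.2 asks about the vaccine and defines its answers by study procedures. Taken literally, it bars *Not Related* for an event clearly caused by a blood draw, and SAP 7.2 can then present that event as related to the booster. The effect is confined to the relatedness breakdowns and the related-event summaries, and arises mainly from the Visit 02 and Day 7 draws.

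Its size cannot be taken from the documents. The illustrative range of about 1 to 33 events rests entirely on the assumed per-draw rates and on the most literal reading. The CRF is not among the documents, so it may already hold a vaccine-specific or a separate procedure field. The case for correcting the text does not depend on the count: as written, the related-event tables may not measure what their labels say, and assessors can diverge.

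**What to change.** - **Protocol 7.2.2:** reword all three category definitions in terms of the CD-JEV booster vaccination, so that they match the heading and instruction.
- **SAP 7.2:** state that the relationship breakdowns and the related-event summaries for immediate reactions, AEs and SAEs use that vaccine-specific rating only.
- **CRF:** if it does not already have one, add a separate field for relationship to other study procedures, such as venipuncture, and list those events separately.

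The cost is a short wording change in each document, possibly one CRF field and one listing, and one more judgement per adverse event.

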### 7.2.3. Reactogenicity

Reactogenicity post vaccination will be assessed in the clinic for 30 minutes, during daily home visits 1 through 6 days following the booster, and during a FSC visit 7 days following the booster. During the daily home visits and FSC visit, the site staff will use a structured reactogenicity reporting form for recording reactogenicity.

Any reactogenicity will be managed in accordance with good medical practices by the clinical study site team, who will assess and treat or refer the child for medical care as appropriate. If needed to monitor or treat reactogenicity, additional study visits may be conducted. If any acute treatment or medical care is required as a result of harm caused by the study vaccine or study procedure, this will be provided by the site free of charge. All children reporting reactogenicity will be followed clinically until the reactogenicity resolves (returns to baseline) or stabilizes. Reactogenicity will be recorded as indicated in the CRF. Reactogenicity likely to be related to the product, whether serious or not, that persists at the end of the trial will be followed up by the PI until resolution or stabilization.

The parents will be instructed to contact the study site staff to report any reactogenicity their child may experience. In the case of a life-threatening event, they will be instructed to seek immediate emergency care.

Where feasible and medically appropriate, parents of children will be encouraged to seek medical care for the child where the study physician is based, and to request that the physician be contacted upon their arrival.

#### **7.2.3.1. Immediate reactions**

All participants will be observed for immediate reactions for 30 minutes after vaccination, with appropriate medical treatment readily available in case of an anaphylactic reaction following the administration of study vaccine. Immediate reactions will be assessed by a study physician or appropriately trained medical staff. All reactions that occur during this time will be recorded on the CRF. Any immediate reaction which meets the criteria for a serious adverse event must also be documented on an SAE form.

#### **7.2.3.2. Local and systemic signs and symptoms**

All participants will be monitored for assessment of local and systemic signs and symptoms occurring from 30 minutes through 7 days post vaccination. Study staff will inquire about specific (solicited) local and systemic signs and symptoms and other unsolicited adverse events.

Using a standardized data collection instrument the following local and systemic signs and symptoms will be documented and graded on predefined scales based on functional assessment or magnitude of reaction. Any local and systemic reaction that meets the criteria for a serious adverse event must also be documented on an SAE form.

#### **Local reactions (at injection site)**

- Ecchymosis (bruising)
- Erythema (redness)
- Edema (swelling)
- Induration (hardness)
- Pain/tenderness

#### **Local ecchymosis, erythema, edema, and induration, if present, will be graded as follows:**

- Grade 1:  $\leq 2.5$  cm in diameter.
- Grade 2:  $> 2.5$  cm in diameter with  $< 50\%$  of surface area of extremity segment involved (upper arm or thigh).
- Grade 3:  $\geq 50\%$  of surface area of extremity segment involved OR ulceration OR secondary infection OR phlebitis OR sterile abscess OR drainage.
- Grade 4: potentially life-threatening consequences (e.g., abscess, exfoliative dermatitis, necrosis involving dermis or deeper tissue).

#### **Injection site pain/tenderness (pain without touching or tenderness as pain when the area is touched), if present, will be graded as follows:**

- Grade 1: pain/tenderness causing no or minimal limitation of use of limb.
- Grade 2: pain or tenderness causing greater than minimal limitation of use of limb.
- Grade 3: pain/tenderness causing inability to perform usual social and functional activities.
- Grade 4: pain or tenderness causing inability to perform basic self-care function OR hospitalization indicated.

**Systemic reactions:**

## General Signs/Symptoms:

- Fever
- Change in eating habits
- Diarrhea
- Sleepiness
- Irritability
- Unusual crying
- Vomiting

**Fever if present will be graded as follows (axillary temperature):**

- Grade 1: 37.5°C to 37.9°C
- Grade 2: 38.0°C to 38.4°C
- Grade 3: 38.5°C to 40.0°C
- Grade 4: >40.0°C

**Change in eating habits, diarrhea, sleepiness, irritability, unusual crying, vomiting, and any other unsolicited reaction occurring through 7 days post booster vaccination will be graded as follows:**

- Grade 1: symptoms causing no or minimal interference with usual social and functional activities.
- Grade 2: symptoms causing greater than minimal interference with usual social and functional activities.
- Grade 3: symptoms causing inability to perform usual social and functional activities with intervention or hospitalization indicated.
- Grade 4: symptoms causing inability to perform basic self-care functions OR medical or operative intervention indicated to prevent permanent impairment, persistent disability, or death.

**7.2.4. Serious adverse events**

An SAE is defined as an AE that meets one of the following conditions:

- Death.
- Life threatening (participant at immediate risk of death). *(The term “life-threatening” in the definition of “serious” refers to an event in which the patient was at risk of death at the time of the event; it does not refer to an event which hypothetically might have caused death if it were more severe.)*
- Requires inpatient hospitalization or prolongation of existing hospitalization.
- Results in a persistent or significant disability or incapacity.
- Important medical events that may not result in death, be life threatening, or require hospitalization may be considered SAEs when, based upon appropriate medical judgment, may jeopardize the participant and may require medical or surgical intervention to prevent one of the outcomes listed in this definition. Medical and scientific judgment should be exercised in deciding whether reporting is appropriate.

All SAEs occurring within 28 days post vaccination must be reviewed and evaluated by a study physician (SAE relationship to study vaccine must be evaluated as outlined in Section 7.2.2) and recorded on an SAE form and reported (as specified in Section 7.3). SAEs, whether serious or not, that persist at the end of the trial will be followed up by the investigator until satisfactory resolution or until the investigator deems the event to be chronic or the participant to be stable. The investigator will document the date of final disappearance of the adverse event

on a data clarification form. All care for SAEs or care required as part of the study will be provided to study participants free of cost.

